# 1 Trial personnel

See protocol cover page for Chief Investigator and Sponsor contact details.

CI: [name]

e-mail: [contact]

Statistician: [name] e-mail: [contact]

Principal Investigatior NELFT: [name]

Email:[contact]

Health Economist: [name]

Email: [contact]

Qualitative researcher lead: [name]

Email: [contact]

Research Assistant: [name]

Email:[contact]

2 Summary	
Objectives:	1. To assess the feasibility and acceptability of a randomised controlled trial of group CST for people with ID and dementia compared to Treatment as Usual. The results of this study will inform the design of a future definitive RCT.
Type of trial:	Feasibility randomised multi-site trial of group CST compared to "Treatment as usual" in participants with dementia and Learning disabilities.
Trial design and methods:	Fifty individuals with ID will be randomised to either the intervention group or control group (treatment as usual). Randomisation will occur after informed consent has been given and baseline assessments completed. Each arm will have 25 participants and be divided into five or more CST groups with up to five participants in each.
	Outcome assessments will include an assessment of cognitive functioning, adaptive functioning and quality of life in individuals with dementia and will also assess the feasibility of collecting the cost-effectiveness measures. A process evaluation will include qualitative interviews with participants, staff and carers to identify aspects of the intervention and study methods including adherence. Any direct quotations used from these interviews in the final publication will be anonymised.
Estimated total trial duration:	30 months
Planned trial sites:	North East London NHS Foundation Trust, East London NHS Foundation Trust, Camden & Islington NHS Foundation Trust, Central and North West London NHS Trust Foundation, London Community Health Care NHS Trust, and Barnet, Enfield & Haringey Mental Health Trust
Total number of	
participants planned:	50
Main inclusion/exclusion criteria:	Inclusion criteria 1. Mild or moderate Learning disabilities 2. ICD-10 diagnosis of mild or moderate dementia

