b. Confirmation of adequate delivery of sessions. Go: 75% of all intervention sessions delivered, Review: 50-74% of all sessions delivered, Stop:<50% of sessions delivered.

c. Acceptability demonstrated through qualitative Interviews with 10 CST participants purposively sampled plus 10 carers and 10 group facilitators (two per NHS site).

Secondary:

1. To assess the fidelity of delivery of the groups by;

a. Recording the number of group CST sessions completed by each participant and level of engagement in the sessions measured using CST participation forms developed alongside the CST manual.

b. Exploring the quality of the intervention delivery according to the recordings and facilitators reflections on delivery fidelity. We will be using a validated CST adherence checklist in order to assess fidelity.

2. To assess the suitability of study outcome measures and determining the primary outcome measure for a future larger RCT:

a. Analysis of completion/ response rates of outcome measures with confirmation these can be collected from the participants.

Go (for each measure): At least 85% of participants fully complete the outcome measure at each time point, Review: 70 - 84% of participants fully complete the measure at each time point, Stop: <70% of participants fully complete the measure at each time point.

b. Examining whether the measures are sensitive to change as a result of the intervention will be established by the preliminary analysis proposed in the statistical analysis section.

3. Collecting resource use information.

Feasibility of collecting resource use data for generating cost information for use in an economic evaluation, including intervention costs. This uses a modified version of the Client Service Receipt Inventory (CSRI) to capture information on health and social care resource use relevant to this population and context, such that published unit costs from NHS Reference Costs and the Personal Social Services Research Unit (PSSRU) Health and Social Care unit costs could be applied to calculate costs in a future full RCT. The modified CSRI is being prepared by the health economist in collaboration with PPI collaborators, clinicians, and other trial team members, and includes information on primary and community health care, medications, routine and emergency hospital care and use of personal social services, provided either by the state or funded privately, as well as financial or related impacts on carers.

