#### 3. Feasibility Randomised Controlled Trial

This will be a single blind, pilot randomised controlled trial of CST delivered by professionals versus treatment as usual. Fifty participants will be randomised to either the intervention group or control group (treatment as usual). Randomisation will occur after baseline assessments are completed. Each arm will have 25 participants and they will be allocated to one CST group with up to five participants in each group.

The duration of the intervention will be 7 weeks. There will be assessments at baseline during the two weeks prior to randomisation, and at the end of the intervention after 8-9 weeks.

Please refer to figure 1 which shows the overall trial design.

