#### 6.3 Recruitment

Participants will be recruited from community learning (Learning) disability teams based within the participating 5 NHS trusts including North East Foundation trust (NELFT), Central North West London Foundation Trust (CNWL), Camden and Islington (C&I), Barnet, Enfield and Haringey (BEH) and East London foundation trust (ELFT). The recruitment will be through the Learning Disabilities Teams in the first instance they will contact possible participants and gain consent to be contacted by the research team. The participants will likely be from multiple types of settings, including people who live in supported living, residential and family homes.

The Paticipants will have been diagnosed (or will be strongly suspected of having dementia) by a clinical psychologist and/or psychiatrist. Psychiatrists/psychologists will be asked to screen their case load for possible participants. Participants will then be approached by members of the multidisciplinary team who work closely with the participant and will discuss the study with the participant and their carer. If they are interested in taking part, they will be provided with an information sheet and their details will be passed on to the trial research assistant or CI. The research assistant will then contact the participant and their carer by phone and will arrange a meeting to

answer questions and to assess eligibility. If the participant (or a consulting carer) agree to taking part then informed consent will be obtained from the participant or consulting carer.

Participant recruitment at a site will only commence when the trial has:

- 1. Been confirmed by the Sponsor (or its delegated representative), and
- 2. Has received REC Favourable opinion and HRA Approval

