# 7 Product/Interventions

## 7.1 Name and description of intervention(s) under investigation

#### Group CST intervention

The intervention will comprise of 14 face to face sessions of CST based on a treatment manual. Each session will begin with discussion of the day, date, weather and location (5 mins) followed by discussion of events in the news or current issues (10 mins) and then the main activity (30 mins). The activities are based around a themed activity (e.g. life story, discussion of current affairs, being creative), which are designed to be mentally stimulating.

Two designated professionals from the Learning Disabilities team will be the group facilitators over a period of 7 weeks, 2 times per week. The groups will be run by professionals in the health team only, carers will not facilitate groups at any point. The activities will be tailored to the abilities and interests of the individuals with ID. Group facilitators will be asked to fill in the group monitoring sheet provided at the back of the CST manual. They will also receive advice and tips on how to adjust parts of the group programme to the level of ability of participants with ID and dementia i.e. using visual cues and replacing words with pictures where possible.

The intervention group will continue to have access to their usual care, which includes input from health and social care professionals, anti-dementia medication and their usual day activities.

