# **11** Statistical Considerations

#### **11.1 Statistical analysis**

Baseline characteristics will be summarized for all participants, the intervention group and control groups separately. Participants' uptake of and adherence to the intervention, as well as follow-up rates, will be summarized and presented as percentages.

Although determining differences in clinical outcomes between the arms is not the primary purpose of this trial, comparisons will be undertaken to investigate the feasibility of studying these outcomes and to calculate estimates for the likely effect sizes and 95% confidence intervals. As recommended in guidelines for good practice for the analysis of pilot studies, the focus of the results will be on the estimates of the treatment effects rather than statistical significance and as such no hypothesis testing will be undertaken. Differences between the two comparison groups will be presented in the form of an unadjusted mean difference for continuous outcomes, and an odds ratio for binary outcomes, with

their associated 95% confidence intervals. Despite the individual randomisation there is group based treatment and therefore consideration will also be made in regard to estimation of the potential intracluster correlation (ICC) coefficient. The estimation of the likely ICC will be able to guide the sample size of a future trial.

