# **11.2** Sample size calculation

This is a feasibility study with no formal power calculation. Instead, a sufficient number of participants need to be recruited in order to determine the attrition and recruitment rates and how these are related to feasibility for a full scale RCT. By setting our target sample size at 50 we will achieve adequate precision around our expected retention rate of 75% (95% confidence interval of 62-86%) to determine the feasibility going forward. Based on our previous study data we are anticipating we will have to screen a maximum of 70 people to reach our sample size.

There is no available data on the use of Cognitive Stimulation Therapy in the treatment of dementia in people with Learning disability. This sample should also provide adequate precision using a confidence interval approach which considers the likelihood of a future definitive study finding a relevant effect size.

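### The protocol says its ICC estimate will guide the size of the definitive trial, but 25 CST participants in a handful of groups of at most five cannot estimate an ICC with useful precision

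*Protocol*

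**What the plan says.** Section 11.1 plans unadjusted mean differences or odds ratios with 95% confidence intervals, then turns to clustering: "Despite the individual randomisation there is group based treatment and therefore consideration will also be made in regard to estimation of the potential intracluster correlation". It closes without qualification: "The estimation of the likely ICC will be able to guide the sample size of a future trial".

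The group structure is in the Summary (section 2): "Each arm will have 25 participants and be divided into five or more CST groups with up to five participants in each". Section 5 repeats the size limit: "they will be allocated to one CST group with up to five participants in each group". The control arm has usual care only (section 7.1), so the grouping is read here as applying to the CST arm.

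Section 11.2 justifies the 50 participants by retention: "By setting our target sample size at 50 we will achieve adequate precision around our expected retention rate". It adds a general remark on effect size and does not mention the ICC. The protocol gives no anticipated ICC and no target precision for it.

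**The concern.** An ICC is estimated from variation between groups, so its precision depends mainly on how many groups there are. Five groups leave four degrees of freedom for the between-group mean square. A study of this size can produce a number, but that number may say little about the true ICC.

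The purpose of the study is to inform a definitive trial, and section 11.1 names the ICC as one of the inputs it will supply. A team that took the statement at face value could carry a zero or negative estimate forward and apply no inflation for clustering, or carry a large chance estimate forward and judge the definitive trial unaffordable.

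**Working it through.** **The plan's own precision figure.** The only one is 62-86% around 75% retention with 50 participants. A Wald interval for 37/50 = 74% is 0.74 ± 1.96 × √(0.74 × 0.26/50) = 61.8% to 86.2%, which matches. It concerns retention, not the ICC.

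**Inputs.**
- CST arm: 25 participants, five or more groups, at most five per group (sections 2 and 5).
- Retention 75% (section 11.2): 25 × 0.75 = 18.75, about 19 analysed, or about 3.75 per group in five groups. I use four.
- True ICC ρ: not in the protocol. Assumed 0.01 to 0.20.

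**Formulas.** For k groups of size m, let F be the ratio of the between-group to the within-group mean square. The one-way ANOVA estimate is (F - 1)/(F + m - 1). F is distributed as c times an F variable on k - 1 and k(m - 1) degrees of freedom, with c = (1 + (m - 1)ρ)/(1 - ρ). The exact 95% limits replace F in the estimate by F/F(0.975) and F/F(0.025). The typical interval is the one obtained at the median estimate.

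**Five groups of four, ρ = 0.05.**
- c = 1.15/0.95 = 1.2105. The median of F on (4, 15) df is 0.878, so the median observed F is 1.063 and the median estimate is 0.063/4.063 = 0.016.
- F(0.975) = 3.804 and F(0.025) = 0.1155, so the two ratios are 0.2795 and 9.204.
- Lower limit: (0.2795 - 1)/(0.2795 + 3) = -0.22. Upper limit: (9.204 - 1)/(9.204 + 3) = 0.67.
- P(estimate ≤ 0) = P(F on (4, 15) df ≤ 1/1.2105 = 0.826) = 0.47.

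**Other ICCs, five groups of four.**

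| True ICC (assumed) | Typical 95% CI | Estimates ≤ 0 |
|---|---|---|
| 0.01 | -0.23 to 0.63 | 54% |
| 0.05 | -0.22 to 0.67 | 47% |
| 0.10 | -0.20 to 0.71 | 39% |
| 0.20 | -0.16 to 0.78 | 26% |

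**Other layouts at ρ = 0.05.**

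| Layout | Typical 95% CI | Estimates ≤ 0 |
|---|---|---|
| Five of five (no attrition) | -0.16 to 0.63 | 46% |
| Seven of four | -0.19 to 0.54 | 44% |
| Eight of three | -0.28 to 0.57 | 45% |

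The last two are generous: they hold 28 and 24 people, against about 19 expected at follow-up.

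**What this means for a sample size.** The CST-arm design effect for groups of five is 1 + 4 × ICC: 1.0 at ICC 0 and 1 + 4 × 0.67 = 3.7 at the upper limit. As an illustration with an assumed standardised difference of 0.4, 80% power and two-sided 5%, 99 per arm (198 in total) are needed without clustering. With one arm clustered and equal arms, the average inflation at the upper limit is (1 + 3.68)/2 = 2.34, so 99 × 2.34 = 231.7, or 232 per arm and 464 in total.

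**What useful precision would take.** The large-sample half-width is 1.96 × √[2(1 - ρ)²(1 + (m - 1)ρ)²/(m(m - 1)(k - 1))]. With ρ = 0.05 and m = 5, a half-width of 0.10 needs k = 51 groups, that is 255 CST participants.

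**Group and trust.** An ICC computed in the CST arm alone also picks up differences between trusts. In a simulation that assumes five trusts with one group of five in each, and trust and group variance shares of 0.05 each, the CST-arm ICC targets 0.10. Using the controls in the same trust removes the trust main effect: the group component averages 0.050, as it should. Its standard deviation is 0.30, however, and 51% of estimates are zero or negative.

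**The case against.** The best defence is that the sentence is modest. Estimation is only to be considered, the ICC is called likely, and to guide a sample size is not to fix it by one point estimate. Section 11.2 never claims precision for the ICC. It is fair that the protocol does not say the point estimate would be used alone. But the sentence says the estimate will be able to do a job, with no caveat, and an interval from below zero to 0.67 cannot do it. Leaving the method to the statistical analysis plan does not help, because no method creates more groups.

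Three stronger readings are tempting, and the documents do not support them.

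- *The reported intervals ignore clustering and are too narrow.* Section 11.1 names no variance method, and unadjusted most naturally refers to covariates. The method may be in the analysis plan. Even a naive interval with five groups of four covers 94%, 93% and 91% at ICCs of 0.05, 0.10 and 0.20 when trusts do not differ. With a trust share of 0.05 and a group share of 0.05 it covers 94.5%, since trust effects largely cancel under randomisation stratified by trust (section 8.2).
- *There is one CST group per trust.* This could be inferred from the "participating 5 NHS trusts" in section 6.3, the interview target of ten facilitators at two per site (section 4), and section 7.1: "Two designated professionals from the Learning Disabilities team will be the group facilitators over a period of 7 weeks, 2 times per week". But the interview target is not a count of groups, the Summary allows more than five groups and lists six trusts, and section 11.3 refers to at least seven services.
- *Group cannot be separated from trust.* Controls exist within each trust, so the trust main effect can be identified. With one group per trust, only group and trust-by-treatment interaction would remain mixed. The difficulty is imprecision, not impossibility.

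**Conclusion.** The concern holds as a point about one sentence. An ICC can be computed from this study, but not precisely enough to guide a sample size. Under assumed true ICCs of 0.01 to 0.20 with five groups of four, the typical upper limit lies between 0.63 and 0.78, and between 54% and 26% of estimates are zero or negative. The conclusion does not depend on exactly five groups, on attrition, or on how groups map to trusts. It does rest on the assumed ICC range and on roughly equal group sizes. The sample-size illustration rests further on the assumed effect of 0.4.

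The recruitment, retention and attendance criteria are unaffected. What changes is a stated output for the definitive trial, so the sentence should be corrected.

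**What to change.** Replace the last sentence of section 11.1. It should say that the ICC in the CST arm will be reported with its 95% confidence interval as a descriptive result, and that the definitive trial will be sized over a pre-stated range of ICCs that includes external estimates from group therapies, not on this study's point estimate.

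Record each CST participant's group, so that the ICC can be computed, and state with the result whether it is a CST-arm-only ICC (which includes trust differences) or has the trust effect removed using the controls.

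The cost is a wording change and one recorded variable. The sample size and visits stay as they are. The downside is a less favourable account of what the study will deliver for the definitive trial.

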# **11.2** Sample size calculation

This is a feasibility study with no formal power calculation. Instead, a sufficient number of participants need to be recruited in order to determine the attrition and recruitment rates and how these are related to feasibility for a full scale RCT. By setting our target sample size at 50 we will achieve adequate precision around our expected retention rate of 75% (95% confidence interval of 62-86%) to determine the feasibility going forward. Based on our previous study data we are anticipating we will have to screen a maximum of 70 people to reach our sample size.

There is no available data on the use of Cognitive Stimulation Therapy in the treatment of dementia in people with Learning disability. This sample should also provide adequate precision using a confidence interval approach which considers the likelihood of a future definitive study finding a relevant effect size.

## **11.3** Planned recruitment rate

We will be recruiting for ten to fifteen months. We estimate that we will recruit four eligible participants each month from at least seven learning disability services in London. If recruitment is anticipated to be slow, we will recruit other centres if necessary.

# 12 Health Economics

## **12.1** Health economic analysis

As this is a feasibility study, the focus will be on the feasibility of collecting data that would be used in a future cost-effectiveness (CEA) alongside a larger future RCT. The aim of that future CEA would be to report the incremental cost per quality-adjusted life-year gained on using group CST compared to treatment as usual, over the time period of the study, from the perspective of the NHS and Personal Social Services.

# 12.2 Quality of life (QOL) and quality-adjusted life years (QALYs)

The EQ-5D-5L is administered to all participants at baseline and at follow-up, to allow reporting of different domains of the participant's health-related quality of life (mobility, self-care, usual activities, pain/discomfort and anxiety/depression) and to see how this has changed in each of the two randomised groups, and to allow utility weights (also called QOL scores or values) to be

calculated from the responses to the EQ-5D-5L using standard algorithms. These QOL values, calculated from the EQ-5D-5L responses captured from participants at baseline and follow-up, are then used to calculate quality-adjusted life-years (QALYs) for participants over the time horizon of the study, using area under the curve methods. QALYs are calculated adjusting for baseline QOL values.

QALYs are the outcome preferred for use in cost-effectiveness analysis by the National Institute for Health and Care Excellence (NICE) when combined together with information on costs. The five questions covering the five domains listed above are followed by a visual analogue score on the second page of the questionnaire, which is not used in health economic analysis but is required to be included for valid administration of the questionnaire.

The feasibility study outcomes here will assess proportions of participants who return completed EQ-5D-5L questionnaires (focusing on the 5 items on the first page and considering the VAS responses separately) at the two timepoints.

## 12.3 Resource use and costs

Besides QALYs, the CEA alongside the future full RCT would require information on costs to the NHS and Personal Social Services (NHS+PSS) of using the group CST intervention and using treatment as usual. Costs would include cost of the intervention in that arm, costs of treatment as usual in both arms, and any other treatment pathway costs, i.e. primary and community health care, medications, routine and emergency hospital care and use of personal social services, provided either by the state or funded privately, as well as financial or related impacts on carers. We would include privately funded care, and impacts on carers, as this is likely to be important in this group, although it would not be included in the base case analysis in the future CEA as it is outside the perspective of the NHS+PSS. We are also collecting baseline costs (i.e. CSRI administered at baseline and carers asked for the participant's preceding 8 weeks of resource use) so that these can be adjusted for in the future analysis.

We will firstly develop an appropriately modified CSRI questionnaire, with input from PPI, clinicians, and others in the trial team, and then use this in our feasibility study to assess the feasibility of collecting resource use data for generating cost information for use in a future RCT in this population and context. Our patient and public involvement collaborators, along with clinicians and other members of the study team, will be involved in modifying the CSRI questionnaire for use in this feasibility study, in terms of tailoring the content and language to make sure it is suitable and that we can try and collect relevant data without over-burdening participants or carers.

The feasibility study outcomes here will assess rates of completion of the different parts of this questionnaire at the two timepoints, and what changes might need to be made to the questionnaire on the basis of the feasibility study outcomes and qualitative feedback, before using an updated and refined version of it in a future larger study.

